## **B. Infusion of LMP-specific T Cells**

1. Nursing staff will ensure that patient has IV access and that the line contains a stopcock for LMP-specific T-cell infusion. Normal saline should be running through the IV line to be accessed.
2. Nursing staff will prepare for emergency procedure by ensuring that oxygen and suction equipment are available in the patient room, according to institution's SOPs, which include availability of emergency drugs and equipment (i.e. epinephrine, diphenhydramine, hydrocortisone or methylprednisolone). In addition, baseline vital signs are documented.
3. The LMP-specific T-cell product will be infused as soon as possible after thawing
4. Two licensed staff will identify the patient by verifying the information on the patient armband and the component with a check of the identification bracelet on the recipient for correct name and hospital number, as per institution's SOP, against the product.
5. The LMP-specific T-cell product will be given through peripheral or central intravenous line over 1 minute and flushed with sterile saline.

## V.

### **Management of Adverse Reactions to LMP-specific T Cell Infusions**

LMP-specific T cells infusions are typically well tolerated but adverse reactions may occur early (within 24 hours of infusion) or late (greater than 24 hours after infusion). Early reactions are usually related to the cryopreserved components.

#### **A. Monitoring Post LMP-specific T Cell Infusion**

Medical staff will assess for any adverse effects for 1 hour post-infusion. Vital signs should be monitored immediately at end of infusion then at 30 and 60 minutes. Patients should remain on continuous pulse oximetry for at least 30 minutes after infusion.

1. Common, mild complications from LMP-specific T-cell infusion include:
  - Mild increase in blood pressure not requiring intervention
  - Mild headache
  - Mild flushing
  - Slight slowing of the heart rate
  - Bad taste in mouth
2. Severe early reactions from LMP-specific T-cell infusion are rare but may include:
  - Acute pulmonary edema and dyspnea
  - Persistent nausea and vomiting
  - Sustained or significant increase in blood pressure
  - Fever
  - Anaphylactic shock

- Bradycardia or cardiac arrest

## B. Management of Early Reactions

Most common, mild early reactions do not require intervention.

1. Management of anaphylaxis: Emergency medications should be ordered in advance and available at the patient's bedside at the time of infusion. Hydrocortisone (or other steroids) should not be administered without approval of physician administering LMP-specific T cells.
  - Hydrocortisone 5-10 mg/kg IV (maximum 500 mg) or methylprednisolone 1-2 mg/kg IV (maximum 125 mg)
  - Epinephrine 0.01 mg/kg IM (preferred) or SubQ (maximum 0.5 mg; 0.01 mL/kg of 1 mg/mL solution, maximum of 0.5 mL)
2. In the event of a severe reaction, the patient should be immediately transferred to emergency room or intensive care unit for intensive monitoring and intervention, which usually includes blood pressure support, steroids, and management of anaphylaxis.

## C. Monitoring and Management of Late Reactions

Late reactions to LMP-specific T cells infusion are rare. The following details regarding signs/symptoms and management, follow (Source: CETI SOP SCTCP-27 Management of Adverse Reactions to T-Lymphocyte Infusions, Version 1.2, Effective Date: 2016-03-21)

1. Late reactions to T-cell infusion may be related to a T-cell engraftment syndrome or cytokine release syndrome (CRS), tumor lysis syndrome, and rarely to contamination of the product.
2. Symptoms and signs of late complications from infusion of T-cell products may include:

Systemic	fever malaise, fatigue myalgias and arthralgias skin rash mimicking acute GvHD general feeling of unwellness disseminated intravascular coagulation (DIC) +/- bleeding macrophage activation syndrome/hemophagocytotic lymphohistiocytosis (HLH) anorexia, nausea, vomiting, diarrhea
Cardiorespiratory	tachycardia blood pressure changes (either hyper- or hypotension) acute pulmonary edema, dyspnea, hypoxia pulmonary infiltrates capillary leak syndrome cardiac dysfunction stress cardiomyopathy (Takotsubo cardiomyopathy) adult respiratory distress syndrome (ARDS)

Hepatic and Renal	weight gain renal impairment azotemia hyperuricemia hepatic impairment – transaminitis, hyperbilirubinemia
Neurological	headache mental status changes confusion delirium hallucinations altered gait seizures encephalopathy mild encephalopathy with reversible splenial lesion syndrome (MERS)

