We will assess the proportion of successes for the primary aim on the first 15 patients assigned to Arm LMP-TC as an interim futility monitoring rule. If fewer than 10 of the first 15 patients are successes for the primary aim (matched and treated within the prescribed timeframe), the Study Committee will assess the reasons for failure and may choose to close the study if it is felt that the reasons are not correctable. If the true success rate is 60%, this rule will be invoked with probability 59.7%; if the true success rate is 80%, the rule will be invoked with probability 6.1%.

We will do real-time monitoring for progression rate at week 10 and for certain protocol-specific toxicities, namely: allograft failure, allograft rejection, cytokine release syndrome grade 3 or higher, and graft versus host disease (see [Appendix V](#)). The monitoring will be done using Bayesian rules with beta priors. The four parameters for each scenario are the two beta distribution parameters ( $\alpha, \beta$ ), the unacceptable probability rate for the event we are monitoring ( $p_0$ ), and the posterior probability that the actual rate exceeds  $p_0$  ( $P(p > p_0 | \text{Data})$ ), which is calculated using the standard Bayesian posterior probability formula

$$P(p > p_0 | \text{Data}) = \frac{\int_{p_0}^1 \binom{n}{x} p^x (1-p)^{n-x} \frac{\Gamma(\alpha + \beta)}{\Gamma(\alpha)\Gamma(\beta)} p^{\alpha-1} (1-p)^{\beta-1} dp}{\int_0^1 \binom{n}{x} q^x (1-q)^{n-x} \frac{\Gamma(\alpha + \beta)}{\Gamma(\alpha)\Gamma(\beta)} q^{\alpha-1} (1-q)^{\beta-1} dq},$$

where  $n$  is the number of observations and  $x$  is the number of events among those  $n$  observations.

We will suspend enrollment to the study if any patient suffers or is suspected to suffer allograft failure or allograft rejection to review the circumstances of the failure or rejection. A recommendation to re-open enrollment might be made if causes other than study therapy were thought to be the primary cause of failure or rejection.

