For cytokine release syndrome and graft versus host disease, the analytic unit for monitoring for protocol-specific toxicities will be the patient-course. Each course where the patient receives the agent or where a protocol-specific toxicity event is observed will be considered in the analysis. We will assume a beta prior distribution with  $\alpha = 0.6$  and  $\beta = 1.4$  and an unacceptable toxicity rate of  $p_0 = 30\%$ . At least once per month, we will calculate the posterior probability (given the data) that the probability of protocol-specific toxicity exceeds the 30% threshold, *i.e.*,  $P(p > 0.3 | \text{Data})$ . If there is a posterior probability of 80% that the toxicity rate is at least 30%, then accrual will be suspended pending review by DSMC. Examples of situations in which this rule will indicate protocol-specific toxicities have been noted and are presented below:

Number of failures	Number of patient-cycles
2	3
3	6
4	8
5	11
6	14
7	17
8	20
9	23
10	26
11	29
12	32
13	35
14	38

Interim monitoring will also be performed to watch for a 20% progression rate at week 10 in newly-diagnosed patients and a 40% progression rate at week 10 for relapsed and refractory patients. For newly-diagnosed patients, the beta parameters will be  $\alpha = 0.52$  and  $\beta = 2.08$ ; and for relapsed and refractory patients the beta parameters will be  $\alpha = 1.04$  and  $\beta = 1.56$ ; if there is a posterior probability of 80% that the progression rate at week 10 is at least 20% for newly-diagnosed patients or 40% for relapsed/refractory patients, then accrual for the respective cohort or cohorts will be suspended pending review by the DSMC. The stopping rule will be triggered as described in the following table:

Number of failures	Number of newly-diagnosed patients	Number of relapsed/refractory patients
2	4	2
3	8	4
4	12	6
5	16	8

6	20	11
7	24	13
8	29	15
9	33	17
10	38	19

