### 3. Management of Late Reactions

- (1) The development of a severe late reaction necessitates immediate notification of the PI and ANHL1522 Study Chair AND (if an outpatient) transfer to the hospital for an urgent medical assessment. It is important to evaluate the patient and initiate therapy as quickly as possible since rapid deterioration is possible.
- (2) Biomarkers: Circulating cytokine levels can serve as biomarkers to diagnose and potentially quantify syndrome severity.
  - (a) IL-6 signaling is major component of severe cytokine release syndrome
  - (b) If possible, cytokine levels should be sent to Viracor prior to starting any anticytokine directed therapy. See [Section 15](#) for corresponding optional research specimen submission.
  - (c) CRP serves as a reliable surrogate for IL-6 bioactivity and levels should be sent pre and post therapy to monitor response
  - (d) Ferritin may also be used in conjunction with CRP monitoring
- (3) The immediate assessment and treatment may also include:
  - (a) Intensive monitoring (BP, cardiovascular monitoring, pulse oximetry or ABG)
  - (b) CXR or CT of chest
  - (c) Steroids – single dose. See #(4) below
  - (d) Microbiological studies (especially blood cultures and virus studies) and initiation of broad-spectrum antibiotics +/- antivirals should be considered.
  - (e) Blood pressure/Cardiovascular support – early institution of inotropic medications. Limit fluid resuscitation to the minimum volume needed to support blood pressure, no more than 20 mL/kg, (up to 1,000 mL), if possible.
  - (f) Fluid management/Renal support – Aggressive diuresis. Institute early involvement of the renal service for fluid management especially if evidence of capillary leak syndrome. Consider infusion of 25% albumin if serum albumin is < 3 g/dL.
  - (g) Respiratory support – supplemental oxygen therapy should be initiated for all hypoxicemic patients. Patients also may require intubation and mechanical ventilation.
  - (h) Management of tumor lysis syndrome if there is laboratory evidence it is occurring.

**(4)** Treatment of the cytokine release syndrome or other T-cell associated adverse reactions must be discussed with the PI and ANHL1522 Study Chair. If the situation is emergent, the first dose of steroids can be given prior to consultation with the PI.

In general, the cytokine release syndrome is managed similarly to engraftment syndrome EXCEPT:

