**IV.4 Statistical Design**

See [Section 9.7](#).

**APPENDIX V: COG STEM CELL COMMITTEE CONSENSUS GUIDELINES FOR ESTABLISHING ORGAN STAGE AND OVERALL GRADE OF ACUTE GRAFT VERSUS HOST DISEASE (GVHD)****Reporting Requirements for Acute GvHD in COG Studies**

In an attempt to standardize reporting of acute GvHD, the COG Stem Cell Transplantation Committee has adopted a modification of guidelines that were originally developed at the University of Michigan.

**Table 1** outlines standard criteria for GvHD organ staging. However, confounding clinical syndromes (such as non-GvHD causes of hyperbilirubinemia) may make staging GvHD in a given organ difficult. In addition, timing of organ specific symptoms affects whether that symptom is more or less likely to be true GvHD. Please refer to **Tables 2 and 3** to assist you in deciding whether to attribute these clinical findings to GvHD, especially in situations where a biopsy is not possible. For additional help, please see the text which follows the tables. **Table 4** reviews the approach to assessing GvHD as acute, chronic, or the overlap between the two.

Finally, *engraftment syndrome* will be reported separately from the GvHD scoring presented below.

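### The Section 9.3 suspension rule does not count a severe late T-cell reaction recorded as engraftment syndrome, and Section 9.5 defines the monitored event differently

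*Combined protocol and SAP*

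**What the plan says.** **Section 9.3 (monitored events).** Real-time toxicity monitoring covers "allograft failure, allograft rejection, cytokine release syndrome grade 3 or higher, and graft versus host disease". Allograft events have their own trigger: "We will suspend enrollment to the study if any patient suffers or is suspected to suffer allograft failure or allograft rejection". CRS and GvHD go to a Bayesian rule, for which "the analytic unit for monitoring for protocol-specific toxicities will be the patient-course". The prior is Beta(0.6, 1.4) and the unacceptable rate is 30%. Accrual is suspended for DSMC review when the posterior probability of exceeding that rate reaches 80%.

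**Section 9.5 (toxicity evaluability).** A protocol-specific toxicity event is a death on therapy at least possibly related to it, or a dose-limiting toxicity. No section defines dose-limiting toxicity.

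**Appendix III, V.C (late reactions).** On causes: "Late reactions to T-cell infusion may be related to a T-cell engraftment syndrome or cytokine release syndrome (CRS), tumor lysis syndrome", and rarely product contamination. One table of signs follows for all of them. It includes fever, capillary leak, hypoxia, macrophage activation syndrome/HLH and "skin rash mimicking acute GvHD". The treatment text keeps the two main causes apart, saying that in general "the cytokine release syndrome is managed similarly to engraftment syndrome", and then lists exceptions.

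**Appendix V (GvHD scoring).** Engraftment syndrome "will be reported separately from the GvHD scoring presented below". Whether a patient has it is left to the local investigator.

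**Section 11.12 (routine reporting).** All adverse events of Grade 3 or higher are reported. CRS, GvHD and allograft events are reported at every grade; engraftment syndrome is not on that all-grades list.

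**The concern.** A numeric stopping rule needs an event definition that two sites would apply in the same way. Here two named entities can explain the same clinical picture, only one is on the rule's list, and nothing operational separates them. A Grade 4 reaction counts under 9.3 if it is recorded as CRS, but not if it is recorded as engraftment syndrome. The GvHD limb does not recover it, because Appendix V takes engraftment syndrome out of GvHD scoring.

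Section 9.5 does not settle the matter. If it governs, a related death counts under any label, but a non-fatal Grade 4 engraftment syndrome counts only if someone decides that it is a dose-limiting toxicity. The study statistician cannot tell from the text which section supplies the numerator.

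At stake is how well the only numeric rule for late reactions to the investigational cells would work, in a mainly paediatric population.

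**Working it through.** **Inputs.** From Section 9.3: prior Beta(0.6, 1.4), limit 30%, posterior threshold 80%, unit the patient-course. Assumed, because the documents do not give them: the true rate of severe late reactions per course, the share recorded under a term that 9.3 counts, independence between courses, and CRS pooled with GvHD in one count.

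**Step 1: reproduce the plan's boundary.** With x events in n courses,

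P(p > 0.30 | x, n) = 1 − F(0.30; 0.6 + x, 1.4 + n − x),

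where F is the beta distribution function. For each x, take the largest n at which this is at least 0.80. The result is 2/3, 3/6, 4/8, 5/11, 6/14, 7/17, 8/20, 9/23, 10/26, 11/29, 12/32, 13/35 and 14/38, which matches all 13 rows of the table in 9.3. The posterior lies between 0.800 and 0.846 at the tabulated n and below 0.80 at n + 1. The arithmetic of the rule is sound; the question is what enters as x.

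**Step 2: what a label does at one look.** Suppose 6 severe reactions in 14 courses.

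| Counted under 9.3 | Posterior | Suspend? |
|---|---|---|
| 6 of 14 | 0.818 | yes |
| 5 of 14 | 0.644 | no |
| 4 of 14 | 0.426 | no |
| 3 of 14 | 0.220 | no |

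On the boundary, one reaction recorded as engraftment syndrome reverses the decision.

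**Step 3: chance of ever suspending.** If the true rate is p and a share s is recorded under a counted term, the rule sees events at rate p × s. An exact binomial recursion, checked after every course up to 30 courses, gives:

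| True severe-reaction rate | All counted | Three quarters counted | Half counted |
|---|---|---|---|
| 20% | 18.9% | 9.4% | 3.7% |
| 30% | 50.1% | 25.3% | 9.4% |
| 40% | 82.3% | 50.1% | 18.9% |
| 50% | 97.0% | 75.6% | 32.8% |
| 60% | 99.8% | 91.9% | 50.1% |

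In the 40% row, the rule sees 0.40 × 0.75 = 30% and 0.40 × 0.50 = 20%. Those entries therefore equal the all-counted values at 30% and 20%.

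**Step 4: sensitivity.** Over 38 courses, the last row of the plan's table, the 40% row becomes 86.8%, 53.1% and 19.2%. Section 9.3 requires a calculation at least monthly, not after every course. Checking only every third course gives 76.5%, 43.1% and 16.4% at 30 courses, so the pattern does not depend on continuous checking.

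**Step 5: cost of counting every label.** With all severe reactions counted, suspension within 30 courses has probability 3.7% at a true combined rate of 10% and 18.9% at 20%.

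**The case against.** **The label does not hide a reaction from everyone.** A reader might infer that the label decides whether a harmful product is detected at all. The documents do not support that. Appendix III requires immediate notification of the Study Chair for any severe late reaction, and Section 11.7 gives the Study Chair ultimate responsibility for identification, grading and attribution. Section 11.12 collects every Grade 3 or higher event, and Section 12.2 sends an unexpected frequency of serious events to the DSMC. This stands. However, none of these routes has a numeric trigger, and 9.3 does not say that the Study Chair assigns the label used in the rule.

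**Section 9.5 counts some events under any label.** This also stands: related deaths are covered there. It would be too strong to say that the plan nowhere counts a fatal engraftment syndrome. For non-fatal reactions, 9.5 rests on an undefined term, and it conflicts with the list in 9.3.

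**MAS/HLH is not a third rival diagnosis.** A reader might place it beside CRS and engraftment syndrome. Appendix III lists it among the signs, not the causes. What remains is that the plan does not say whether such a picture counts as CRS.

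**The two syndromes can be told apart.** Appendix III says that cytokine levels help diagnosis and names IL-6 signaling as a component of severe CRS. It gives no cut-off and asks for levels only where possible. Appendix V describes engraftment syndrome in cord blood and mismatched transplantation, while Section 3.2.5 excludes prior stem cell transplant. That makes the Appendix V description hard to apply here, but Appendix III still offers the term for these patients. The agent section is redacted, and the source SOP and CRFs are not in the documents, so criteria may exist there.

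**The illustration is hypothetical.** This is fair. Appendix III calls late reactions rare, and Section 2.5.6 reports one significant complication in over 65 recipients of donor-derived EBV-specific T cells. A 40% rate is not a forecast. It shows how the rule behaves above its own 30% limit, where it is meant to act.

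**Conclusion.** The point holds as a gap in the event definition and a conflict between two sections. Under 9.3 as written, a severe late reaction recorded as T-cell engraftment syndrome is outside the Bayesian rule, and 9.5 gives a different and incomplete definition.

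At an assumed true rate of 40%, the chance of suspension within 30 courses falls from 82% with all reactions counted to 50% with three quarters counted and 19% with half counted. These figures rest on the assumed rate and label split, on independent courses, on pooling CRS with GvHD (which the plan does not state), and on a check after every course. The boundary itself is correct. The allograft suspension and the reviews without a numeric threshold remain in place, so the finding concerns the sensitivity of one rule, not an absence of safety oversight. The change should be made, and it needs only wording.

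**What to change.** 1. Use one event definition in both 9.3 and 9.5: a Grade 3 or higher T-cell-related systemic reaction counts once per patient-course, whether recorded as CRS, T-cell engraftment syndrome or MAS/HLH. Keep the prior, the 30% limit and the 80% threshold, so the boundary table stands.
2. In 9.5, define dose-limiting toxicity or remove it, and say how related deaths enter the rule.
3. State in 9.3 whether CRS-type reactions and GvHD form one pooled count or two separate ones.

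The cost is protocol and CRF wording, plus somewhat more reviews. If all such events are counted, accrual would be suspended within 30 courses in about 4% of trials at a true combined rate of 10%, and in about 19% at 20%, which is still below the 30% limit. The second figure is not negligible and should be accepted knowingly. No change to treatment or to the management of reactions is implied.

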### 3. Management of Late Reactions

- (1) The development of a severe late reaction necessitates immediate notification of the PI and ANHL1522 Study Chair AND (if an outpatient) transfer to the hospital for an urgent medical assessment. It is important to evaluate the patient and initiate therapy as quickly as possible since rapid deterioration is possible.
- (2) Biomarkers: Circulating cytokine levels can serve as biomarkers to diagnose and potentially quantify syndrome severity.
  - (a) IL-6 signaling is major component of severe cytokine release syndrome
  - (b) If possible, cytokine levels should be sent to Viracor prior to starting any anticytokine directed therapy. See [Section 15](#) for corresponding optional research specimen submission.
  - (c) CRP serves as a reliable surrogate for IL-6 bioactivity and levels should be sent pre and post therapy to monitor response
  - (d) Ferritin may also be used in conjunction with CRP monitoring
- (3) The immediate assessment and treatment may also include:
  - (a) Intensive monitoring (BP, cardiovascular monitoring, pulse oximetry or ABG)
  - (b) CXR or CT of chest
  - (c) Steroids – single dose. See #(4) below
  - (d) Microbiological studies (especially blood cultures and virus studies) and initiation of broad-spectrum antibiotics +/- antivirals should be considered.
  - (e) Blood pressure/Cardiovascular support – early institution of inotropic medications. Limit fluid resuscitation to the minimum volume needed to support blood pressure, no more than 20 mL/kg, (up to 1,000 mL), if possible.
  - (f) Fluid management/Renal support – Aggressive diuresis. Institute early involvement of the renal service for fluid management especially if evidence of capillary leak syndrome. Consider infusion of 25% albumin if serum albumin is < 3 g/dL.
  - (g) Respiratory support – supplemental oxygen therapy should be initiated for all hypoxicemic patients. Patients also may require intubation and mechanical ventilation.
  - (h) Management of tumor lysis syndrome if there is laboratory evidence it is occurring.

**(4)** Treatment of the cytokine release syndrome or other T-cell associated adverse reactions must be discussed with the PI and ANHL1522 Study Chair. If the situation is emergent, the first dose of steroids can be given prior to consultation with the PI.

In general, the cytokine release syndrome is managed similarly to engraftment syndrome EXCEPT:

- As the patient received an investigational T-cell agent, steroids may not be considered first line therapy and anti-IL-6 directed therapy MAY be given without first starting steroids.
- When managing CRS, anti-IL-6 directed therapy should be initiated before anti-TNF $\alpha$  directed therapy.
- Caution is required when using tocilizumab in the setting of hepatic impairment.

**(5)** If treatment with a biological agent is necessary, the order of priority will usually be:

- Tocilizumab
- Infliximab (anti-TNF $\alpha$ )
- Etanercept (soluble TNF $\alpha$  receptor inhibitor)

Drug	Dosing	Duration
Tocilizumab	<30 kg: 12 mg/kg IV ≥30 kg: 8 mg/kg (maximum 800 mg) IV	One dose, with repeat dosing if no improvement observed within 24-48 hours.
Infliximab	10 mg/kg IV	One dose, may give second 3-4 days later
Etanercept	0.4 mg/kg (maximum 25 mg) SubQ	One dose, may give second 3-4 days later

